Diagnosis and Main Inclusion Criteria	Adult patients with a diagnosis of breast cancer and who are scheduled to receive chemotherapy with a life expectancy greater than or equal to 12 months.
Study Product, Dose, Route, Regimen	
India ink (Carlo Erba) and electron paramagnetic resonance oximetry measurements.
 
Standard, clinical electrophysiologic tests: nerve conduction study and needle electromyography.
 
SUDOSCAN measure of sudomotor function.

Duration administration of	Ink administered once, EPR oximetry measurements and standard electrophysiologic studies at three distinct time points over the course of chemotherapy. As many as five measurements will be done for each time point.
Statistical Methodology	Correlations between peripheral tissue oximetry and clinical & electrophysiologic measures of CIPN and EPR assessments of hypoxia and response to oxygen. Descriptive statistics of NFL changes over time. Correlations between NFL and peripheral neuropathy assessments.

1 Introduction

This document is a protocol for a human research study. This study is to be conducted according to US and international standards of Good Clinical Practice (International Conference on Harmonization ICHE6), the Code of Federal Regulations Title 21 especially device related parts 803 and 812, and other applicable government regulations and Institutional Research Board (i.e., Dartmouth's Committee for the Protection of Human Subjects, CPHS) research policies and procedures.

1.1 *Background*

As medical surveillance and effective therapies improve the survivability of cancer, the number of people living with a history of cancer will increase drastically. "Quality of survival" is increasingly being recognized as an important mission of cancer care. Chemotherapy induced peripheral neurotoxicity (CIPN) is a common, potentially severe and dose-limiting adverse effect of cancer chemotherapeutic agents. A major shortfall in management of subjects with CIPN is the absence of (i) early predictors for those at greatest risk of CIPN, and (ii) sensitive biomarkers to identify disease onset at an earlier stage.

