Patients will be informed that they may not personally benefit from participation in this study; however, the study aims to help patients in the future. The identification of a biomarker that not only provides information regarding the underlying pathophysiology, but also allows for early prediction of those patients at greatest risk of developing chemotherapy-induced peripheral neurotoxicity, is of significant benefit to patients undergoing chemotherapy. Early identification/prediction can help oncologists tailor and advise patients about side effects they may expect to develop and help them make informed choices about their therapy. Advancements in the understanding of the pathogenesis of this neurotoxicity will lead to better therapies, both in the prevention and the management of CIPN.

2 Study Objectives

The overall objective is to extend the pathophysiologic understanding of CIPN and identify better biomarkers for patients at greatest risk of developing early and/or severe or refractory CIPN.

Primary Objectives:

The primary objective of the study is: to prospectively compare peripheral tissue oxygenation response between patients who later develop CIPN, and those who do not.

Secondary Objectives:

The secondary objectives of the study are to: (i) establish the feasibility of the approach, (ii) to evaluate the utility of longitudinal clinical and electrophysiologic assessments and (iii) to describe changes in biomarkers of axonal degeneration including neurofilament light chain over the course of chemotherapy

Specific Aim #1: *Adapt the existing clinically established techniques for EPR oximetry to measurements of oxygen to be relevant to the pathophysiology of CIPN.* In the proposed research, we will use an India ink injection and obtain an initial oximetry reading assessing local oxygen metabolism. The objective of this aim will be to establish feasibility of the approach and obtain preliminary data for a more definitive and statistically robust cohort. Five measurements will be done within each study visit window to improve the strength of the readings.

Specific Aim #2: Establish a pre-exposure neurologic phenotype and baseline tissue oximetry in cancer patients scheduled to receive neurotoxic chemotherapy. In order to assess a potential biomarker for CIPN, it must be correlated to metrics of CIPN that can be reliably followed and quantitated as a function of progression and severity.

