Specific Aim #3: Re-evaluate neurologic phenotype and tissue oximetry in symptomatic patients after exposure to a standard regimen of neurotoxic chemotherapy. Neurologic phenotype and EPR oximetry will be re-assessed at mid-chemotherapy treatment regimen or at the onset of symptoms. The assessments will be repeated at the completion of chemotherapy and will provide longitudinal data for comparison against baseline characteristics.

Specific Aim #4: In order to develop a proposal for a statistically robust cohort, use pilot data to (i) inform regarding the feasibility and potential utility of EPR oximetry as a CIPN biomarker, (ii) focus on the most sensitive metrics to follow, and (iii) to suggest trends of correlation in sub-metrics. This study is designed for the collection of preliminary data and to establish the feasibility and optimization of the EPR oximetric technique in CIPN. It is anticipated that this data will guide a larger study for which additional, external funding will be sought.

Specific Aim #5: Describe changes in serum NFL levels over the course of chemotherapy to determine if NFL can be used as a biomarker for axonal damage in patients who develop CIPN. NFL will be measured at baseline, before each round of chemotherapy and at the completion of chemotherapy. Changes in NFL will be compared between patients who develop CIPN and those that do not.

3 Study Design

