Visit 2 will be scheduled at the onset of CIPN symptoms or at the mid-point of chemotherapy treatment. If a patient reports symptoms of CIPN to their nurse or physician, or if the patient's provider suspects CIPN is present prior to midpoint of therapy, the subject will be scheduled for Visit 2, in which the electrophysiologic and clinical assessments are standard of care. For patients who do not show signs of CIPN by the mid-point of their treatment, the study staff will coordinate a visit for clinical and electrophysiological assessment. These assessments will be identical to the tests conducted at Visit 1.

Patients will also return to the Department of Radiation Oncology for their second round of EPR measurements. The continuous EPR will take approximately 30 minutes (~10 minutes breathing room air, ~10 minutes of enriched oxygen, ~10 minutes breathing room air again). As many as five measurements will be made in the ± 18 days surrounding the electrophysiologic assessments at Visit 2.

6.4 Visit 3

Visit 3 will take place no sooner than one week after the completion of chemotherapy. The procedures for this visit will be the same as Visits 1 and 2: patients will receive clinical and electrophysiological assessments, and EPR oximetry measurement. As many as five measurements will be made in the ± 18 days surrounding the electrophysiologic assessments at Visit 3.

6.5 *Unscheduled EPR Oximetry Readings*

Subjects who develop symptoms of CIPN may experience fluctuations of these symptoms. Unscheduled EPR oximetry measurements may be conducted if a subject experiences change in these symptoms as the PI sees as appropriate.

6.6 *Blood Draws for Serum Biomarker Assessment*

Prior to the start of chemotherapy, prior to each scheduled chemotherapy treatment, and after the completion of chemotherapy, patients will provide a blood sample (2 tablespoons) for

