7.1 Sample Size Determination

This pilot study is designed for proof of concept and to establish the bedrock for a future trial with a more robust sample. The secondary objective of this pilot is to demonstrate effective recruitment, screening, assessment processes, and high participant retention. We will assess the proportion of potential participants that: meet inclusion criteria, consent to participate, and complete all assessments.

Thirty (30) patients will be enrolled in the study, and it has been estimated that ten (10) patients will develop CIPN during their taxane treatment. Accurate incidence of CIPN varies significantly; the average incidence is 70% (Seretny et al., 2014), with ranges from 30% to 90%. A conservative estimate is that 30%-50% of patients in this trial will develop symptoms of neuropathy during their chemotherapy treatment. Development of CIPN will be determined based on the results of their neurologic assessments. For data analysis, the patients will be divided by this CIPN status into two groups. Primary endpoints are continuous metrics: Endpoint 1) neurological phenotyping involves electrophysiological assessment (e.g. nerve conduction, EMG readings, SUDOSCAN results), and Endpoint 2) tissue oximetry involves the EPR measures). The mean levels of each electrophysiological or oximetry metric will be assessed between the two groups of patients (with CIPN vs. without) over time (at timepoints: before, mid-, and post-chemotherapy) using repeated measures ANOVA. This method will also assess the within-subject changes in the electrophysiological and EPR oximetry metrics over time, from baseline through post-chemotherapy, as well as the interaction between CIPN status and time. With 15 patients per group, we anticipate that we will have 80% power to detect a between-groups difference in longitudinal EPR oximetry measures by CIPN status of 28%, assuming a correlation of 0.5 among repeated measures, a standard deviation of 25%, alpha=0.05. The within-subjects and interaction tests are estimated to be able to detect an 8.5% change over time, with these same parameters (calculated using G*Power 3.1.9.2).

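### Visit 2 pools readings taken at symptom onset with readings taken before it, so the mid-chemotherapy ranking can credit a marker of present symptoms as an early predictor

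*Combined protocol and SAP*

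**What the plan says.** Visit 2 has two triggers. Section 6.3 says: "Visit 2 will be scheduled at the onset of CIPN symptoms or at the mid-point of chemotherapy treatment". If a patient reports symptoms, or the provider "suspects CIPN is present prior to midpoint of therapy, the subject will be scheduled for Visit 2"; everyone else is seen at the midpoint. Specific Aim #3 agrees: "Neurologic phenotype and EPR oximetry will be re-assessed at mid-chemotherapy treatment regimen or at the onset of symptoms". Up to five EPR readings may fall within 18 days either side of the electrophysiologic assessment. Section 6.5 allows further unscheduled readings because "Subjects who develop symptoms of CIPN may experience fluctuations of these symptoms".

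The analysis has one label for all of this. In Section 7.1, "Development of CIPN will be determined based on the results of their neurologic assessments", and group means are compared "over time (at timepoints: before, mid-, and post-chemotherapy) using repeated measures ANOVA". The terms named are status, time and their interaction. The same section ranks metrics by the size and t-test p-value of the status difference at the pre- or mid-chemotherapy timepoint, in order to find those that pick out early the patients who will later be diagnosed. Nothing in the analysis refers to cycles received, time since first dose, or whether a reading was taken before or after onset. Section 5.3 has chemotherapy progress followed, but for scheduling.

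The primary objective in Section 2 is "to prospectively compare peripheral tissue oxygenation response between patients who later develop CIPN, and those who do not". Section 1.1 names two separate gaps in current practice: the lack of "early predictors for those at greatest risk of CIPN, and (ii) sensitive biomarkers to identify disease onset at an earlier stage".

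**The concern.** When Visit 2 takes place depends on symptoms, and symptoms are closely tied to the grouping variable. Two separate problems follow.

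1. **Interpretation (main).** The CIPN group's mid-chemotherapy mean mixes patients who already have symptoms with patients who do not yet. A metric that changes only when symptoms appear will separate the groups at Visit 2 and can be carried forward as an early predictor. Prediction and onset detection are both legitimate aims here, but the ranking does not keep them apart.
2. **Exposure (secondary).** Patients seen early are read after less chemotherapy. A metric that drifts with exposure in everyone then differs by status at Visit 2 for no other reason.

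What is at stake is mostly the choice of metrics for the larger study, which is the purpose of this pilot under Specific Aim #4. The primary between-groups test is less exposed, because it averages over three timepoints.

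**Working it through.** **The plan's own figure.** Section 7.1 states 80% power for a 28% difference with 15 per group, SD 25%, correlation 0.5 and alpha 0.05. For the between-groups F-test, the effect size is (28/25)/2 = 0.56 and the noncentrality is 0.56² × 30 × 3 / (1 + 2 × 0.5) = 14.1 on F(1, 28). That gives 95.2% power, and 80% is reached at 21.6 points. So the printed figure does not reproduce from its stated inputs. A one-visit t-test with 10 vs 20 gives 79.7% at 28 points. That is a separate matter and this point does not rest on it.

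**Inputs.** From Section 7.1: 10 of 30 expected to develop CIPN (so 10 vs 20), SD 25, correlation 0.5, alpha 0.05 (taken as two-sided). Assumed, because the documents give none of them:
- p1, p0: shares moved early with and without CIPN (p0 = 0 unless stated)
- D: drift over the whole course
- f: fraction of the course received at a moved visit
- S: shift present only while symptomatic

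**Symptom state.** The spurious Visit 2 difference is the symptomatic share times S. With half of the CIPN patients symptomatic and S = 25 (one SD), it is 0.5 × 25 = 12.5 points. The Visit 2 t-test is significant in 21.6% of simulated trials when those patients are moved early. At a fixed midpoint with persisting symptoms it is 21.4%, and 9.6% if the mean shift has halved by then. The early visit therefore adds to the effect only if symptoms fade.

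**Exposure.** The spurious Visit 2 difference is b = (p1 − p0) × D × (f − 0.5). The between-groups test carries b/3. Rejection of the status-by-time interaction (20,000 simulated trials, nominal 5%):

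| D | p1, p0, f | b (points) | Interaction |
|---|---|---|---|
| 8.5 | 0.5, 0, 0.3 | −0.85 | 5.1% |
| 8.5 | 1, 0, 0.2 | −2.55 | 5.8% |
| 25 | 0.5, 0, 0.3 | −2.5 | 5.8% |
| 25 | 1, 0, 0.3 | −5 | 7.6% |
| 50 | 0.5, 0, 0.2 | −7.5 | 10.2% |
| 50 | 1, 0, 0.2 | −15 | 32.8% |
| 50 | 0.5, 0.2, 0.2 | −4.5 | 5.9% |

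Between-groups rejection is 5.2-5.6% in the D = 25 rows, and 6.3-9.3% in the D = 50 rows with p0 = 0. The 8.5 is the change over time that Section 7.1 says it can detect. It is a scale, not a forecast of drift. If 8.5 points were reached already by the midpoint, with half the CIPN group read at half that exposure, the Visit 2 t-test at 10 vs 20 rejects in 5.6%. If all were read at a third of it, the figure is 8.8%.

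**Both together.** With p1 = 0.5, D = 50 and f = 0.2, exposure contributes −7.5. S = +12.5 adds 0.5 × 12.5 = 6.25, leaving −1.25 points and 5.2% rejection. S = −12.5 gives −13.75 points and 24%. The pooled difference cannot be read as either effect.

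**Ranking.** Chance that a non-predictor has a larger |t| at Visit 2 than a true 12.5-point predictor (p1 = 0.5, 100,000 trials):

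| Non-predictor | All readings | Pre-onset only |
|---|---|---|
| Pure noise | 30% | 37% |
| Symptom-only, S = 25 | 48% | 37% |
| Drift, D = 50, f = 0.2 | 37% | 37% |

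**Cost of restricting to pre-onset readings.** If half the CIPN group is moved, 10 vs 20 becomes 5 vs 20. The difference detectable at 80% power rises from 28.1 to 36.6 points, and power for 25 points falls from 70% to 48%.

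**Visit 3 (separate, minor).** Sections 6.1 and 6.4 place the visit at least seven days after treatment ends, with an EPR window of 18 days either side of the electrophysiologic assessment. Read literally, 7 − 18 = −11: a reading up to 11 days before completion.

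**The case against.** The strongest reply is that the timing of Visit 2 does little harm. That largely stands. A reader might infer that the early visit itself creates the false signal, but 21.6% against 21.4% shows the symptom effect is the same at a fixed midpoint if symptoms persist. A reader might also infer that exposure bias undermines the primary test. On the plan's own scale it does not, and the 33% case needs two-SD drift, every CIPN patient moved and no one else. Since the trigger is a report or suspicion while status comes from neurologic assessment, patients without CIPN can be moved too, which shrinks the bias.

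Nor do the figures show that ranking on pre-onset readings is better. It helps against a one-SD symptom shift, makes no real difference for the drift case, and is worse against noise.

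It is also fair that an onset reading has proper uses. Specific Aim #3 re-evaluates symptomatic patients on purpose, Section 1.1 wants earlier onset detection, and a reading at first symptoms can precede a formal diagnosis. Symptom scores are collected at every visit, so part of the information exists. What remains is that the ranking rule, followed as written, does not separate these uses from prediction.

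On Visit 3, a reader might infer that pre-completion readings are planned. EPR is listed as a procedure of a visit with a one-week floor, so day −11 arises only if the window overrides the floor. This is an ambiguity.

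**Conclusion.** The point holds as a matter of interpretation and is worth fixing. Pooling onset and pre-onset readings under one mid-chemotherapy label lets a marker of present symptoms be ranked as an early predictor. That follows from the text without any assumed number. Its size does not: the 48% against 30% rests on an assumed one-SD symptom shift in half of the CIPN patients and a half-SD true predictor. The exposure problem is secondary. It is about 5-6% rejection for drift near 8.5% over the course, and material only when drift approaches two SD and the share moved differs strongly by status. The baseline contrast is untouched. The documents do not support a claim that the primary between-groups comparison is invalid or that Visit 2 must be held at another time.

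**What to change.** - At each EPR and nerve conduction reading, record cycles received or days since first taxane dose. Record the date of first reported or suspected symptoms.
- Flag each reading, not each visit, as before onset or at/after onset, since five readings over ±18 days can straddle onset. Flag unscheduled readings in the same way.
- Keep the all-readings mid-chemotherapy comparison and ranking. Report the pre-onset comparison beside it as a descriptive sensitivity analysis.
- Rest any claim of prediction on baseline and pre-onset readings. Use onset readings for Specific Aim #3 and onset detection.
- Add a sensitivity mixed model with actual exposure in place of the visit label, and check for curvature.
- Separately, reconcile the Visit 3 floor with its EPR window, so that no reading dated before the last treatment is analysed as post-chemotherapy.

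The cost is dates and analysis wording, with no new visit or measurement and no change to when Visit 2 is held. Chemotherapy progress is already followed under Section 5.3. The onset date should be captured prospectively, because it may not be recoverable later. The drawbacks are real: the pre-onset comparison is smaller, keeps only later-onset CIPN patients, and is empty if all of them are moved, so it must not replace the all-readings ranking. If every CIPN patient and no one else is moved, the exposure adjustment rests on the assumed shape of the drift.

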6.7 Blood Draw for Genetic Research (Optional)

Patients will be given the option to provide whole blood to a biobank for CIPN. Willing participants will give an additional tube of blood (1-2 tablespoons) to be stored in the CIPN biobank. All attempts will be made by the study team to obtain the blood sample at the patient's next standard blood draw. In the event that this is not feasible, the patient will have the option of having a separate blood draw done for study purposes. A tube will be filled and labelled with the patient ID # and the study #. Samples will be stored in the Department of Neurology -80 degree freezer for storage and eventual Deoxyribonucleic acid (DNA) extraction. The samples will remain in the bank until they are used for another CPHS approved research study. An electronic document will hold the patient Id – study ID code. Stored samples will not have patient information on the label. The electronic code will be stored on an encrypted DHMC drive and not removed from Dartmouth-Hitchcock servers.

7 Statistical Plan

7.1 Sample Size Determination

This pilot study is designed for proof of concept and to establish the bedrock for a future trial with a more robust sample. The secondary objective of this pilot is to demonstrate effective recruitment, screening, assessment processes, and high participant retention. We will assess the proportion of potential participants that: meet inclusion criteria, consent to participate, and complete all assessments.

Thirty (30) patients will be enrolled in the study, and it has been estimated that ten (10) patients will develop CIPN during their taxane treatment. Accurate incidence of CIPN varies significantly; the average incidence is 70% (Seretny et al., 2014), with ranges from 30% to 90%. A conservative estimate is that 30%-50% of patients in this trial will develop symptoms of neuropathy during their chemotherapy treatment. Development of CIPN will be determined based on the results of their neurologic assessments. For data analysis, the patients will be divided by this CIPN status into two groups. Primary endpoints are continuous metrics: Endpoint 1) neurological phenotyping involves electrophysiological assessment (e.g. nerve conduction, EMG readings, SUDOSCAN results), and Endpoint 2) tissue oximetry involves the EPR measures). The mean levels of each electrophysiological or oximetry metric will be assessed between the two groups of patients (with CIPN vs. without) over time (at timepoints: before, mid-, and post-chemotherapy) using repeated measures ANOVA. This method will also assess the within-subject changes in the electrophysiological and EPR oximetry metrics over time, from baseline through post-chemotherapy, as well as the interaction between CIPN status and time. With 15 patients per group, we anticipate that we will have 80% power to detect a between-groups difference in longitudinal EPR oximetry measures by CIPN status of 28%, assuming a correlation of 0.5 among repeated measures, a standard deviation of 25%, alpha=0.05. The within-subjects and interaction tests are estimated to be able to detect an 8.5% change over time, with these same parameters (calculated using G*Power 3.1.9.2).

We are particularly interested in identifying the metrics that allow the early identification of patients who go on to have a clinical diagnosis of CIPN. Within the pre- or mid-chemotherapy timepoints, the metrics that show a combination of the largest magnitude difference and lowest t-test p-value by CIPN status will be prioritized for future study. For primary endpoint 3), we will also use Pearson correlation to assess the relationship between metrics, for example, EPR oximetry will be assessed vs. a continuous CIPN metric (e.g. nerve conduction, temperature sensation, vibratory sensation) within a timepoint, e.g. post-chemotherapy). With n=30 patients, we anticipate having 80% power to detect at least a 33% difference in the means of a metric using an independent samples t-test comparing patients with CIPN vs. without, or a regression slope of 0.66 among continuous metrics, with a standard deviation of 0.25, and alpha of 0.05. This data will guide a larger study for which additional, external funding will be sought.

The potential utility of the EPR measures will be assessed in these CIPN patients using either a minimum within-subjects increase over time in the tissue oximetry measure of (e.g. 5%) compared to baseline, or a Pearson r threshold (e.g. -0.3) for the correlation between the tissue oximetry and electrophysiological measures of sensory or motor nerve conduction.

8 Safety and Adverse Events

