3.2 Primary Study Endpoints

The primary endpoint identified for the purposes of driving the sample size and primary analysis is: **the between-groups difference in longitudinal EPR oximetry measures by CIPN status.**

4 Subject Selection and Withdrawal

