Subjects will also receive their baseline electrophysiological assessment at this visit. See section 1.2.1 for device information. Sensory conductions may include sural, medial plantar and dorsal sural antidromic testing with assessment of peak to peak amplitudes of sensory nerve action potentials and sensory conductions. Motor conductions may also be tested in tibial and peroneal nerves with measurement of baseline to peak amplitude of the compound muscle action potential, motor conduction velocities, and distal motor latencies. Recording will be performed from the extensor digitorum brevis and tibialis anterior muscles. Additional or different nerves may be tested at the discretion of the examiner. Temperature will be controlled and data compared with normative age-matched reference data. Testing will be performed by EMG technicians trained in

performing electrodiagnostic studies or the study neurologist. Testing will be repeated for each nerve to ensure verifiable amplitudes. The SUDOSCAN recordings will be made with both the patients' hands and feet.

Subjects will report to the Department of Radiation Oncology at Dartmouth-Hitchcock Medical Center for EPR oximetry. The EPR Center's established procedures for the injection of India ink will be followed. Subjects will receive an injection of ink in the foot over the distal fourth dorsal interosseous toe web. Subjects may require 2 or more days after the injection in order for the ink to settle before the first EPR oximetry measurement can be performed. As many as five measurements will be performed prior to beginning chemotherapy.

The standard oximetry measurement procedure consists of acquiring continuous EPR scans to characterize 1) baseline tissue oxygen levels 2) tissue oxygen levels in response to inhalation of enriched oxygen mixture and 3) response to oxygen levels in tissue to discontinued breathing of enriched oxygen. The total time for one measurement is approximately 30 minutes: approximately 10 minutes while breathing room air, then ~10 minutes while breathing enriched oxygen by non rebreather face mask, followed by ~10 minutes while resuming breathing room air.

6.3 Visit 2

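### Section 3.2 names one primary endpoint and Section 7.1 names three, so the plan does not settle what the primary analysis is

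*Combined protocol and SAP*

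**What the plan says.** Section 3.2 uses the singular: "The primary endpoint identified for the purposes of driving the sample size and primary analysis is" followed by "the between-groups difference in longitudinal EPR oximetry measures by CIPN status". The Study Summary and Section 2 each state one primary objective to match, a comparison of tissue oxygenation between patients who later develop CIPN and those who do not.

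Section 7.1 uses the plural and numbers its endpoints:

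- First: "Primary endpoints are continuous metrics: Endpoint 1) neurological phenotyping involves electrophysiological assessment", with nerve conduction, EMG and SUDOSCAN as examples. This is a list of examples, not a closed set.
- Second: "Endpoint 2) tissue oximetry involves the EPR measures", again plural and not enumerated.
- Third, further down: "For primary endpoint 3), we will also use Pearson correlation to assess the relationship between metrics". The metrics to be correlated are also given only as examples.

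On testing, Section 7.1 says "The mean levels of each electrophysiological or oximetry metric will be assessed between the two groups of patients" by repeated measures ANOVA at three time points. The same model is to assess change within subjects and the interaction of CIPN status with time. An alpha of 0.05 appears in the two power statements and nowhere else. The plan gives no order of testing and no multiplicity adjustment, and it does not say which section governs.

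**The concern.** A reader of Section 3.2 expects one result to decide the primary question. A reader of Section 7.1 can treat a nerve conduction difference, a SUDOSCAN difference, any EPR quantity or a correlation as primary. The label matters because Section 7.1 says the data will guide a larger study for which outside funding will be sought. If many quantities share the label, a chance finding on one of them can carry more weight in that later design than it deserves, and nobody can say afterwards how many comparisons stood behind it.

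**Working it through.** **1. The plan's own figure.** Section 7.1 claims 80% power for a 28% between-groups EPR difference, with 15 per group, three time points, correlation 0.5 among repeated measures, SD 25% and alpha 0.05. For the between-groups term, lambda = f² × N × m / (1 + (m − 1) × rho), with f = (28/25)/2 = 0.56, N = 30, m = 3 and rho = 0.5. So lambda = 0.3136 × 90 / 2 = 14.1 on F(1, 28). Power is 95.2%, and the difference detectable with 80% power is 21.6%. The stated pair does not reproduce. That is a separate matter, and nothing below depends on it. What counts here is that the ANOVA between-groups power claim concerns EPR only.

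**2. How many tests are primary?** The documents give no count, so three assumed counts are shown:

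- **3 tests:** one for each endpoint numbered in Section 7.1.
- **9 tests:** the three electrophysiological examples in Section 7.1, three EPR phases, and the three example metrics for correlation with EPR (nerve conduction, temperature sensation, vibratory sensation).
- **17 tests:** three sensory nerves × 2 measures = 6; two motor nerves × 3 measures = 6; SUDOSCAN hands and feet = 2; EPR phases = 3. The total is 6 + 6 + 2 + 3 = 17. Sections 1.2.1a and 6.2 say only that these nerves may be tested and leave others to the examiner, so 17 is a construction and not the plan's list.

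**3. Chance of at least one p < 0.05 when nothing truly differs.** With independent tests it is 1 − 0.95^k:

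- k = 3: 1 − 0.857 = 14.3%
- k = 9: 1 − 0.630 = 37.0%
- k = 17: 1 − 0.418 = 58.2%

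For correlated tests the values come from simulating equally correlated two-sided tests. The 10 versus 20 split follows the Section 7.1 expectation of ten CIPN cases among thirty. Correlations between metrics are assumed, since the 0.5 in Section 7.1 is among repeated measures of one metric. The correlation tests in the count of 9 are treated like the others. Simulated values are good to about one percentage point.

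| Tests | Correlation 0 | 0.5 | 0.8 |
|---|---|---|---|
| 3 | 14% | 13% | 10% |
| 9 | 37% | 27% | 17% |
| 17 | 58% | about 40% | 22% |

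These figures take one test per metric. Extra time points and the other ANOVA terms would add to them.

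**4. Does Section 3.2 alone give 5%?** Not yet. It refers to EPR measures in the plural. Section 6.2 describes each session as "acquiring continuous EPR scans to characterize 1) baseline tissue oxygen levels 2) tissue oxygen levels in response to inhalation of enriched oxygen mixture", plus a third phase after the enriched oxygen stops. The Study Summary speaks of oxygenation levels, while Section 2 speaks of oxygenation response. Testing all three phases at 0.05 returns the first row of the table, 10-14%. The rate is 5% only when one EPR quantity and one model term are fixed in advance.

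**The case against.** The best case for the plan is that this is a pilot whose purpose is to rank metrics. Section 3.1 lists electrophysiological characterisation, EPR as a biomarker and their correlation together as main purposes, so the three endpoints in Section 7.1 are no accident. Specific Aim 4 asks for the most sensitive metrics and for trends. Section 7.1 prioritises metrics by size of difference together with the lowest p-value, and judges EPR utility by example thresholds (a 5% within-subject increase, or r of -0.3). For that purpose the family-wise error rate is not the main operating characteristic. Most of this stands, and strict family-wise control is not asked for here.

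A partial hierarchy also exists. Section 3.2 says which endpoint drives the primary analysis, and the ANOVA power statement in Section 7.1 describes the same EPR comparison. That also stands, and it shows which way to resolve the conflict. It does not remove the conflict: if Section 3.2 governs, Section 7.1 mislabels two of its three primary endpoints.

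A reader might infer three stronger things that the documents do not support:

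- That any metric with p < 0.05 would make the study positive. No such decision rule is written.
- That the plan sets 0.05 for each metric. Alpha appears only in the power statements, and no significance level for the analysis of Endpoint 1 is given.
- That the protocol lists 17 metrics, making the error rate 41-58%. The count is assumed, and higher correlation or fewer tests gives much lower figures.

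**Conclusion.** The contradiction is plain on the face of the text and needs no assumption: one primary endpoint in Section 3.2, three in Section 7.1, two of them open-ended, with nothing to rank them. Confidence in that part is high.

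The size is less certain. It rests on three assumptions: every test is run at 0.05, no true effects exist, and the counts and correlations are those in the table. On that footing the chance of at least one nominally significant primary result runs from about 10% to 58%, against 5% for a single pre-named test. Even the smallest count, one test per declared endpoint, gives two to three times the nominal rate.

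It would go too far to say that the study has no defensible primary claim. The EPR between-groups comparison is identifiable from Sections 2, 3.2 and the power statement. What is missing is agreement between the sections and a single named EPR quantity. The point should be corrected, but it does not undermine the pilot.

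**What to change.** In Section 7.1:

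1. State that the Section 3.2 EPR between-groups comparison is the only primary endpoint.
2. Name the one EPR quantity to be analysed: one of the three phases, or one response measure derived from them. Say how the readings at a time point, of which there may be as many as five, are reduced to it.
3. Name the one repeated measures ANOVA term tested at 0.05. The between-groups CIPN effect is the natural choice, because Section 3.2 and the power statement already describe it and the power statement treats the within-subject and interaction tests separately.
4. Relabel Endpoint 1, the third primary endpoint, the other EPR phases and the other ANOVA terms as exploratory. Report them as estimates with 95% confidence intervals, and state how many comparisons were made.

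The cost is wording in Section 7.1, and fewer results can be called primary. No patients, visits or analyses are added, and the ranking of metrics for future study can go ahead as exploratory work.
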